**Table 1: Baclofen Titration and Dosing Schedule**

Day	Morning Dose	Afternoon Dose	Bedtime Dose	Total Daily Dose
1-2	placebo	10 mg	10 mg	20 mg
3-4	10 mg	10 mg	10 mg	30 mg
5-6	10 mg	10 mg	20 mg	40 mg
7-9	20 mg	20 mg	20 mg	60 mg
10-11	20 mg	20 mg	30 mg	70 mg
12-94	30 mg	30 mg	30 mg	90 mg
95-97	20 mg	20 mg	30 mg	70 mg
98-100	10 mg	20 mg	20 mg	50 mg
101-103	placebo	10 mg	20 mg	30 mg
104-106	placebo	placebo	10 mg	10 mg
107	placebo	placebo	placebo	0 mg

### **5.3 Method for Assigning Subjects to Treatment Groups**

Randomization blocks will be prepared by the statistician and provided to the Investigational Drug Services. A minimization random assignment procedure will be used to match subjects on the key moderator (DDD) (< 14 DDD or  $\geq 14$  DDD for men and <10 DDD or  $\geq 10$  DDD for women. Randomization will be linked to sequential study number which subjects receive as they enroll in the study.

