### **5.4 Preparation and Administration of Study Drug**

UNC Hospital's Investigational Drug Services (IDS) will purchase baclofen tablets in 10 mg and 20 mg strengths and create opaque baclofen capsules and matching placebo that will be inserted into blister packs. The 10 mg baclofen/placebo capsule and the 20 mg baclofen/placebo capsule will be color coded so physicians can make finer dose adjustments if needed. All used and unused blister cards will be returned to the IDS. [name], the study biostatistician, will prepare the randomization schedule and include blocking by high/low DDD ( $\geq 14$  for men and ( $\geq 10$  DDD for women). The randomization schedule will be given to IDS personnel; investigators will not have access to this information. If a medical or other emergency necessitates breaking the blind, IDS personnel will provide the identity of the medication to the PI or another medical study team member.

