## **5.6 *Blinding of Study Drug (if applicable)***

The study biostatistician, will prepare the randomization schedule and include blocking by high/low DDD ( $\geq 14$  for men and  $\geq 10$  DDD for women) and by gender. The randomization schedule will be given to IDS personnel; investigators will not have access to this information. If a medical or other emergency necessitates breaking the blind, IDS personnel will provide the identity of the medication to the PI or another medical study team member.

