### **Randomization**

A minimization random assignment procedure will be used to match subjects on the key moderator (DDD).(< 14 DDD or  $\geq$ 14 DDD for men and <10 DDD or  $\geq$ 10 DDD for women. This minimization random strategy for assignment to condition was developed specifically for research studies where the number of matching criteria is large for the number of subjects in a study (White et al,1978). In contrast to stratified randomization, which aims for equal numbers of subjects in each treatment for every possible combination of the prognostic variables, the minimization method restricts its aim to equalizing treatment numbers at the different levels of each variable taken separately. Thus, with minimization, there is not the problem that there are more combinations of variables than planned participants. Minimization is particularly superior to stratified randomization when the number of strata is large in comparison with the number of subjects (i.e., not enough subjects to fill every cell). The data analysis team has used this procedure in previous clinical trials and have found no significant differences on the matching criteria in any study (Linehan et al. 2008).

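### Randomisation is described in ways that cannot all be true, and the primary model does not pre-specify the allocation factors

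*Combined protocol and SAP*

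**What the plan says.** The allocation procedure appears in five places in the combined protocol and SAP.

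- **Section 5.3** opens with "Randomization blocks will be prepared by the statistician and provided to the Investigational Drug Services". It then names minimisation on two-level DDD (cut-offs 14 for men, 10 for women) and closes with "Randomization will be linked to sequential study number which subjects receive as they enroll in the study".
- **Section 5.4**: the biostatistician "will prepare the randomization schedule and include blocking by high/low DDD", and the schedule goes to the Investigational Drug Services (IDS).
- **Section 5.6** repeats this and adds a factor: "for women) and by gender. The randomization schedule will be given to IDS personnel".
- **Section 6, Randomization**: "A minimization random assignment procedure will be used to match subjects on the key moderator (DDD". Minimisation is set against stratified randomisation, because "the minimization method restricts its aim to equalizing treatment numbers at the different levels of each variable taken separately". The method is said to have been "developed specifically for research studies where the number of matching criteria is large for the number of subjects in a study", yet DDD is the only factor named.
- **Section 6, Initial Treatment Visit**: drug is dispensed according to the participant's randomisation block.

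No block size, minimisation probability, or rule tying the study number to the DDD stratum is given.

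Two statistical passages depend on this. Section 7.1 bases the Aim 2 power on 40 per arm, split 20 high and 20 low DDD. In Section 7.2 the primary summary model contains treatment only. Other covariates enter if they differ at baseline or are judged important confounders, with gender and race as examples. Aim 2 adds a continuous pre-treatment drinking measure, labelled HDD, to all models.

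**The concern.** Minimisation assigns each participant from the totals accrued so far, so it cannot exist as a block schedule written beforehand and given to IDS. Section 6 itself presents minimisation as the alternative to stratification, while 5.4 and 5.6 describe a stratified schedule. Gender is a factor in 5.6 and nowhere else in the allocation text. The statistician and IDS could run different procedures and each be following some section of the protocol.

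Three things are at stake:

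- The allocation cannot be reproduced from the document.
- Its predictability cannot be judged. Minimisation on one factor with no random element would fix every third assignment within a stratum.
- The analysis cannot be matched to the design, because the reader does not know whether gender is a design factor, and the primary model does not commit to the DDD stratum in any case.

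**Working it through.** **1. Can the descriptions be merged?** Prepared blocks within DDD strata, with a separate number series per stratum, would satisfy 5.4 and most of 5.3, but not minimisation. Minimisation would satisfy Section 6, but not a schedule handed over in advance. Adding gender satisfies 5.6 and departs from 5.3, 5.4 and 6. No single procedure fits all five places.

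**2. Reproduce the Aim 2 power (Section 7.1).** Inputs: effect 1.2 SD in the high-DDD group and 0 in the low group, 20 per cell, attrition 16.2%. Two-sided alpha of 0.05 is assumed, as none is stated for Aim 2. The contrast is (mean of the two baclofen arms minus placebo) in high DDD, minus the same in low DDD.

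- Variance = 1/20 + 1/40 + 1/20 + 1/40 = 0.15
- Noncentrality = 1.2/√0.15 = 3.10, with 120 − 6 = 114 df
- Power = 86.7%, as stated
- With attrition each cell is 20 × 0.838 = 16.76, the variance is 0.179, and power is 80.2%, as stated

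**3. Recompute power under each scheme.** Simulation with 120 participants, 60 of them high DDD. Assumptions not in the documents: block size 6, 55% men, minimisation probability 0.8 or 1.0, and attrition equal across cells. There were 4,000 replicates for block and simple schemes and 1,500 for minimisation.

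| Scheme | Largest cell deviation from 20: mean (95th percentile) | Mean power, no attrition | Mean power, 16.2% attrition |
|---|---|---|---|
| Blocks within DDD | 0 (0) | 86.7% | 80.2% |
| Blocks within DDD by gender | 1.0 (2) | 86.7% | 80.1% |
| Minimisation on DDD, probability 0.8 | 0.9 (2) | 86.7% | 80.1% |
| Minimisation on DDD, no random element | 0 (0) | 86.7% | 80.2% |
| Minimisation on DDD and gender, probability 0.8 | 0.9 (2) | 86.7% | 80.1% |
| One block list by study number, ignoring DDD | 3.1 (6) | 86.1% | 79.5% |

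For the last row the 5th percentiles are 85.0% and 78.0%. Simple randomisation, which the protocol does not describe, serves as an outer bound: 85.5% and 78.8%.

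**4. Hand check of the single-list case.** If arms of exactly 40 are drawn without regard to DDD, the high-DDD count per arm is hypergeometric (120, 60, 40). Its SD is √(40 × 0.5 × 0.5 × 80/119) = 2.59, with a 95% range of 15 to 25. Suppose placebo has 16 high and 24 low, and each baclofen arm 22 and 18. The variance is 1/16 + 1/44 + 1/24 + 1/36 = 0.155, and power is 85.7%, or 79.0% with attrition.

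**5. Recruitment mix.** With 13 high and 27 low in every arm, so perfect balance between arms, power is 82.1%, or 74.9% with attrition.

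**The case against.** A reader might infer that the balance Aim 2 relies on is not assured, and that DDD imbalance would pass directly into the treatment estimate. The documents do not support that.

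- Every allocation description that names a factor names DDD. The sequential-number sentence follows directly on the one that matches on DDD, and nothing says there is only one list. DDD is known from screening, so numbering within strata is an ordinary reading.
- Even the single-list reading costs only 0.6 to 0.7 point of power.
- The 20/20 split depends first on recruiting 50% heavy drinkers. Step 5 shows that missing this quota could cost far more than the choice of algorithm.
- Chance imbalance under random allocation is not bias, and the unadjusted standard error already allows for it. Section 7.2 also has a route for gender and pre-treatment drinking to enter the models.
- Predictability matters only to someone who knows earlier assignments. The trial is double-blind and investigators have no access to the schedule. The protocol also calls its minimisation random, so an unstated probability does not make it deterministic.

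All of this stands, and it removes the claim about Aim 2. It does not remove the contradiction in the text. Nor does it make the covariate rule adequate: adding whatever differs at baseline is decided after the data are seen, and the HDD measure under Aim 2 is neither labelled nor scaled as the DDD stratum used for allocation.

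**Conclusion.** The point holds as one of specification and reproducibility. Sections 5.3, 5.4, 5.6 and 6 give incompatible accounts of allocation, gender is a factor in one of them only, and the parameters needed to run any of them are missing. DDD is the intended balancing factor throughout. Any scheme that uses it holds mean Aim 2 power within about 0.1 point of the stated 86.7% and 80.2%, and the worst reading of the text lowers these to 86.1% and 79.5%. That drop is noticeable only because the attrition-adjusted figure has almost no reserve above 80%. The power figures rest on the assumptions listed in the working and on 60 of the 120 participants being high DDD.

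Separately, the primary summary model does not pre-specify the variables used in allocation. Doing so would align analysis with design and remove a data-dependent choice. The gain in precision cannot be sized, because the documents do not say how strongly DDD predicts the outcome.

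**What to change.** 1. State one algorithm and one factor list, identically, in 5.3, 5.4, 5.6 and 6 (including the dispensing sentence under Initial Treatment Visit). Either permuted blocks within DDD strata, with or without gender, or minimisation with a stated random element would serve, and the power results do not favour one over the other. Give the block sizes or the minimisation probability, and say that the DDD stratum is determined before the assignment is drawn. If minimisation is kept, replace the reference to a prepared schedule with a statement of who runs the procedure and how IDS receives each assignment. If blocks are kept, drop the minimisation rationale.

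2. In Section 7.2, pre-specify the allocation factors (high/low DDD stratum, and gender if it is retained) as covariates in the primary summary model and the mixed model. This replaces the treatment-only model and the rule of adding measures that differ at baseline.

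The cost is protocol wording and one or two degrees of freedom. Nothing changes for participants.

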### **5.4 Preparation and Administration of Study Drug**

UNC Hospital's Investigational Drug Services (IDS) will purchase baclofen tablets in 10 mg and 20 mg strengths and create opaque baclofen capsules and matching placebo that will be inserted into blister packs. The 10 mg baclofen/placebo capsule and the 20 mg baclofen/placebo capsule will be color coded so physicians can make finer dose adjustments if needed. All used and unused blister cards will be returned to the IDS. [name], the study biostatistician, will prepare the randomization schedule and include blocking by high/low DDD ( $\geq 14$  for men and ( $\geq 10$  DDD for women). The randomization schedule will be given to IDS personnel; investigators will not have access to this information. If a medical or other emergency necessitates breaking the blind, IDS personnel will provide the identity of the medication to the PI or another medical study team member.

### **5.5 Packaging**

Tablets 10 mg – oval, white, scored (imprinted Lioresal on one side and 10 twice on the scored side)  
Bottles of 100.....NDC 0028-0023-01  
Unit Dose (blister pack)  
Box of 100 (strips of 10).....NDC 0028-0023-61

Tablets 20 mg – capsule - shaped, white, scored (imprinted Lioresal on one side and 20 twice on the scored side)  
Bottles of 100.....NDC 0028-0033-01  
Unit Dose (blister pack)  
Box of 100 (strips of 10).....NDC 0028-0033-61

Do not store above 30°C (86°F). Dispense in tight container (USP).

## **5.6 *Blinding of Study Drug (if applicable)***

The study biostatistician, will prepare the randomization schedule and include blocking by high/low DDD ( $\geq 14$  for men and  $\geq 10$  DDD for women) and by gender. The randomization schedule will be given to IDS personnel; investigators will not have access to this information. If a medical or other emergency necessitates breaking the blind, IDS personnel will provide the identity of the medication to the PI or another medical study team member.

### **5.6.1 *Receipt of Drug Supplies***

Upon receipt of the of the study treatment supplies, an inventory must be performed and a drug receipt log filled out and signed by the person accepting the shipment. It is important that the designated study staff counts and verifies that the shipment contains all the items noted in the shipment inventory. Any damaged or unusable study drug in a given shipment (active drug or comparator) will be documented in the study files.

### **5.6.2 *Dispensing of Study Drug***

The Investigational Drug Service (IDS) at UNC will be responsible for dispensing baclofen or placebo for this trial.

Participants will record their pill taking in calendar-style diaries that will be provided and collected at each visit. Additionally, baclofen and placebo will be distributed in blister packs that will be returned to the study coordinator, who will reconcile any unused medication from the returned blister packs with participants' diary records.

### **5.6.3 *Return or Destruction of Study Drug***

At the completion of the study, there will be a final reconciliation of drug shipped, drug consumed, and drug remaining. This reconciliation will be logged on the drug reconciliation form, signed and dated. Any discrepancies noted will be investigated, resolved, and documented prior to return or destruction of unused study drug. Drug destroyed on site will be documented in the study files.

## **6 *Study Procedures***

Potential participants will be recruited from the Raleigh, Durham, and Chapel Hill areas by screening patients at Freedom House and via advertising and referrals. Freedom House is a local publically funded detoxification center. Approximately 350 alcohol dependent individuals per year are admitted to Freedom House. These individuals have been screened to minimize risk of more serious withdrawal problems such as DTs or seizures and individuals with serious psychiatric problems such as suicidal behavior or psychosis or serious medical problems that require acute care are not admitted. Patients at Freedom House receive medical or social detoxification depending on symptom severity. A CIWA-Ar driven protocol using lorazepam has been utilized there. The average length of stay at Freedom House is 4 days. This population represents treatment seeking individuals who are more likely to have higher levels of physical dependence than our traditional trial population recruited by advertising. This is a very important point as this population may be the one that responds best to baclofen (see Leggio et al, 2010).

Individuals at Freedom House will be screened in person whereas those who respond to advertisements will have a preliminary telephone screening conducted by the study coordinator.

Individuals who appear eligible, as determined by the investigative team, will be scheduled to come to the UNC Hospitals for more comprehensive screening. Prior to full screening, individuals will read and sign the informed consent and be given a copy for their records. A breathalyzer test using an Alco-Sensor III breathalyzer machine (Intoximeters, Inc., St. Louis, MO) will be administered (must be 0.00 gms/dl to give informed consent). Height and weight will be measured and BMI calculated. Medical personnel will conduct a medical history and examination including a neurological examination. Over-the-counter and prescription medication use will be recorded. The Fagerstrom Test for Nicotine Dependence (Heatherton et al, 1991) will be administered to smokers. Laboratory evaluations will include complete blood count (CBC) with differential; chemistries including bilirubin, AST, ALT, Alkaline Phosphatase, GGT, sodium, potassium, chloride, blood urea nitrogen, creatinine, and glucose; and urinalysis and urine toxicology. A carbohydrate deficient transferrin (CDT) sample will be drawn. CDT samples will be stored frozen and then shipped in batches of 40 to [name] lab in Charleston, South Carolina for assay. With subjects' permission a sample of blood will also be obtained to archive for possible future genetic analyses. Women will be given a urine pregnancy test (Ub-HCG) at screening and at weeks 4, 8, 12 and 16. Trained interviewers will conduct the psychiatric screening interview using the M.I.N.I. (Sheehan et al., 1999) and the SCID Substance Use Disorders Module to establish DSM-IV criteria for alcohol dependence and to assess for other substance use disorders (First, 2002). The study coordinator will conduct the pretreatment 90-day Timeline Followback interview (TLFB, Sobell et al, 1988) and potential participants will complete the Spielberger State/Trait Anxiety Inventory (SSTAI) (Spielberger et al (1969)), the Drinker's Inventory of Consequences (DrInC, Miller et al, 1995) the FHAM to assess family history of alcohol problems (Rice et al, 1995), the University of Rhode Island Change Assessment Scale (URICA, McConaughy et al, 1989) to assess motivation level, the Penn Alcohol Craving Scale (PACS, Flannery et al 1999) to assess craving, and the Insomnia Severity Index (Bastien et al, 2001) to assess sleep problems. Additionally, potential participants will fill out a short evaluation of their treatment goals. This visit should take about 3 hours.

### **Randomization**

A minimization random assignment procedure will be used to match subjects on the key moderator (DDD).(< 14 DDD or  $\geq$ 14 DDD for men and <10 DDD or  $\geq$ 10 DDD for women. This minimization random strategy for assignment to condition was developed specifically for research studies where the number of matching criteria is large for the number of subjects in a study (White et al,1978). In contrast to stratified randomization, which aims for equal numbers of subjects in each treatment for every possible combination of the prognostic variables, the minimization method restricts its aim to equalizing treatment numbers at the different levels of each variable taken separately. Thus, with minimization, there is not the problem that there are more combinations of variables than planned participants. Minimization is particularly superior to stratified randomization when the number of strata is large in comparison with the number of subjects (i.e., not enough subjects to fill every cell). The data analysis team has used this procedure in previous clinical trials and have found no significant differences on the matching criteria in any study (Linehan et al. 2008).

### **Initial Treatment Visit**

Individuals meeting all inclusion/exclusion criteria will be informed and scheduled for the initial treatment visit within 10 days. Eligible individuals will not be required to abstain from drinking alcohol prior to randomization though those from Freedom House will be post-detoxification and may be alcohol free. The study coordinator will administer a breathalyzer test (BAC must be  $\leq$ 0.04 gms/d), conduct the TLFB interview, and ask participants to complete the PACS and the SSTAI. The study physician will evaluate withdrawal symptoms using the CIWA-Ar and note the use of medications. A 1-week blister pack of baclofen/placebo with written instructions will be dispensed from the Investigational Drug Services according to the randomization block along with a 1-week back-up blister pack in case of delayed appointments or lost doses. Participants also will be given a calendar style

diary to track pill taking, drinking, and any side effects and a Baclofen Instruction Sheet along with a wallet card detailing potential problems should the individual require emergency medical treatment. Finally, participants will receive Medical Management from a trained clinician. This visit should be completed in about 1.25–1.5 hours.

It is important to uptitrate and downtitrate the dose of baclofen to minimize side-effects. We will parallel the titration schedule used by Franklin et al (2009) in their study of 20 mg of baclofen given four times per day. In the latter study, baclofen was well tolerated without significant differences between baclofen and placebo groups—for the chief side-effect of sedation, the baclofen group had 20 mild, 4 moderate and 0 severe reports of sedation compared to 4 reports of mild sedation and 0 reports of either moderate or severe sedation with placebo (Franklin et al, 2009). Our titration schedule for the 90 mg/d dose is shown in Table 1. The 30 mg/d arm will reach 30 mg/d at day 3 and titrate down starting at day 101.

**Table 1: Baclofen Titration and Dosing Schedule**

Day	Morning Dose	Afternoon Dose	Bedtime Dose	Total Daily Dose
1-2	placebo	10 mg	10 mg	20 mg
3-4	10 mg	10 mg	10 mg	30 mg
5-6	10 mg	10 mg	20 mg	40 mg
7-9	20 mg	20 mg	20 mg	60 mg
10-11	20 mg	20 mg	30 mg	70 mg
12-94	30 mg	30 mg	30 mg	90 mg
95-97	20 mg	20 mg	30 mg	70 mg
98-100	10 mg	20 mg	20 mg	50 mg
101-103	placebo	10 mg	20 mg	30 mg
104-106	placebo	placebo	10 mg	10 mg
107	placebo	placebo	placebo	0 mg

### **Subsequent Treatment Visits**

At study week 1, participants will receive a 2-week supply of baclofen or placebo. After that, baclofen or placebo will be dispensed at study weeks 3, 6, 8, 10, 12 and 14. The pill taking, drinking, and side effects diaries will be collected and new diaries distributed at each visit. Medical monitoring will be conducted by study physicians and will consist of review of vital signs, concomitant medication use, and general inquiries into side effects. At each visit, participants will also be given a breathalyzer test (must be < 0.04 gms/dl), TLFB interview, and complete the PACS. Medication management sessions will be conducted at each visit. At weeks 4 and 10 blood will be drawn for evaluation of liver functioning and glucose. At weeks 4, 8, and 12 urine pregnancy testing will be conducted. At week 16 or early termination, a physical will be conducted along with CBC, chemistries, and urinalysis. Participants will be encouraged to attend Alcoholics Anonymous (AA) during treatment

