### **Post-Treatment Follow-up**

One month following termination or treatment completion, the study coordinator will call each participant, conduct a TLFB interview, and inquire about general health and adverse events.

Subject participation should average around 21 weeks including screening, randomization, the active medication phase and the one month follow-up. Variations will occur for individual subjects depending upon their schedule, missed visits, etc.

Table 1 Study Schedule of Assessments

	Screen Visit	Initial Visit	Wk 1	Wk 2	Wk 3	Wk 4	Wk 6	Wk 8	Wk 10	Wk 12	Wk 14	Wk 16
Informed consent	X											
Physical/Neuro exam	X											X
Pregnancy testing	X #					X †		X †		X †		X †
CBC & chemistries	X					X*		X*		X*		X*
Baclofen Trough Level						X						
CDT Level	X											X
Archived blood sample	X											
Urinalysis/ toxicology	X											X**
M.I.N.I./SCID	X											
DrInC, FMAST	X											
STAI Y-1 (State)	X	X	X	X	X	X	X	X	X	X	X	X
STAI Y-2 (Trait)	X											X
CIWA		X										
Sleep Survey	X	X				X		X		X		X
URICA	X											
Vital signs	X	X	X	X		X	X	X	X	X	X	X
Dispense Baclofen/placebo		X	X		X	X	X	X	X	X	X	
Adverse events		X	X	X	X	X	X	X	X	X	X	X
Concomitant meds	X	X	X	X	X	X	X	X	X	X	X	X
Breathalyzer	X	X	X	X	X	X	X	X	X	X	X	X
TLFB	X	X	X	X	X	X	X	X	X	X	X	X
PACS	X	X	X	X	X	X	X	X	X	X	X	X
MM session		X	X	X	X	X	X	X	X	X	X	X

# Serum pregnancy test, \*\* or early termination \* Creatinine, glucose, AST, ALT, GGT, and bilirubin only; †Urine Pregnancy Test only;

\*\*Urinalysis only. Questionnaires: Alcohol/Substance Use Disorders Module (SCID); Alcohol Dependence Scale (ADS); Drinker's Inventory of Consequences (DrInC); Timeline Followback interview (TLFB) F-MAST Family Assessment Scale, the University of Rhode Island Change Assessment Scale (URICA), Penn Alcohol Craving Scale (PACS).

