#### **Abnormal Laboratory Values**

A clinical laboratory abnormality should be documented as an adverse event if any one of the following conditions is met:

- The laboratory abnormality is not otherwise refuted by a repeat test to confirm the abnormality
- The abnormality suggests a disease and/or organ toxicity
- The abnormality is of a degree that requires active management; e.g. change of dose, discontinuation of the drug, more frequent follow-up assessments, further diagnostic investigation, etc.

Because baclofen is principally renally excreted individuals with elevated creatinine or reduced GFR will be excluded. Additionally, creatinine and a liver profile will be monitored at 4, 8 and 12 weeks and, if creatinine is elevated or AST/ALT levels  $> 5 \times$  ULN, medication will be stopped. Participants will be given a card to carry with them to inform health care personnel that the individual may be on baclofen.

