## **10 Study Monitoring, Auditing, and Inspecting**

### **10.1 Study Monitoring Plan**

The investigator will allocate adequate time for such monitoring activities. The Investigator will also ensure that the monitor or other compliance or quality assurance reviewer is given access to all the above noted study-related documents and study related facilities (e.g. pharmacy, diagnostic laboratory, etc.), and has adequate space to conduct the monitoring visit.

We will follow our standard protocol for monitoring of clinical trials. First, subjects are screened to exclude those who might have an increased risk associated with study participation, e.g. renal failure, diabetes mellitus, pregnancy. Pregnancy will be initially screened using a blood test with increased sensitivity compared to urine tests. Second, subjects are monitored on a regular basis with visits at post-randomization weeks 1, 2, 3, 4, 6, 8, 10, 12, 14 and 16. At these visits vital signs are taken and subjects are asked about any side-effects or problems that they are having. At weeks 4, 8, 12 and at termination a liver profile and creatinine level are examined. Participants with elevated creatinine or AST/ALT levels  $> 5X$  ULN or a bilirubin  $> 1.5$  ULN will have their medication tapered and stopped and will be monitored by study physicians. In these instances another liver profile and creatinine will be drawn within 2-4 weeks.

Participants will be contacted by telephone 4 weeks after the final trial visit to ascertain drinking behavior and any physical or psychiatric problems. Individuals with clinically significant problems will be referred for appropriate psychiatric or medical treatment.

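### The visit text puts on-treatment safety bloods at weeks 4 and 10 and omits creatinine, while the schedule table and sections 8.1 and 10.1 require weeks 4, 8 and 12 with creatinine

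*Combined protocol and SAP*

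**What the plan says.** Four places in the protocol schedule the on-treatment safety bloods.

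- **Section 6, Subsequent Treatment Visits:** "At weeks 4 and 10 blood will be drawn for evaluation of liver functioning and glucose". The same paragraph then deals with the end of the study: "At week 16 or early termination, a physical will be conducted along with CBC, chemistries, and urinalysis".
- **Section 6, Study Schedule of Assessments:** the row "CBC & chemistries" is marked at screening and, with an asterisk, at weeks 4, 8, 12 and 16. Week 10 is blank. The asterisk is explained as "Creatinine, glucose, AST, ALT, GGT, and bilirubin only".
- **Section 8.1, Abnormal Laboratory Values:** "creatinine and a liver profile will be monitored at 4, 8 and 12 weeks". The same sentence stops medication if creatinine is elevated or AST/ALT exceeds 5 times the upper limit of normal (ULN).
- **Section 10.1, Study Monitoring Plan:** "At weeks 4, 8, 12 and at termination a liver profile and creatinine level are examined". The next sentence tapers and stops medication on the same creatinine and AST/ALT limits, and adds bilirubin above 1.5 times ULN.

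No text gives an order of precedence among these places.

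**The concern.** The narrative of the treatment visits is an instruction that site staff could reasonably work from, and on this point it disagrees with the rest of the protocol. It adds a draw at week 10 that appears nowhere else, drops weeks 8 and 12, and leaves out the one analyte that tracks renal function.

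The protocol treats renal function as a safety matter. Reduced estimated GFR is an exclusion criterion, section 8.1 points to renal excretion, and an elevated creatinine ends medication. A stopping rule of that kind works only if the measurement is scheduled while the patient is still taking the drug. The AST/ALT and bilirubin limits depend on the same draws, so they too would be checked less often under the visit text.

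The conflict also creates deviations whichever text a site follows. A draw at week 10 departs from the table, and draws at weeks 8 and 12 depart from the visit text.

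**Working it through.** The plan gives no figure of its own to reproduce here. The check sets the four places side by side and then counts days.

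**1. Comparison**

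| Place in the protocol | On-treatment weeks | Creatinine named? |
|---|---|---|
| Section 6, Subsequent Treatment Visits | 4, 10 | No |
| Section 6, schedule of assessments | 4, 8, 12 (then 16) | Yes, in the footnote |
| Section 8.1 | 4, 8, 12 | Yes |
| Section 10.1 | 4, 8, 12 (then termination) | Yes |

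Only week 4 is common to all four.

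**2. Are the table columns read correctly?** The pregnancy-test row has marks in the same columns as the chemistries row. The text of section 6 separately places that test at screening and weeks 4, 8, 12 and 16. The column alignment is therefore sound.

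**3. Could the visit text's wording cover creatinine implicitly?** That is hard to sustain. The screening panel in section 6 lists creatinine as an analyte in its own right, next to glucose and apart from the liver tests: "sodium, potassium, chloride, blood urea nitrogen, creatinine, and glucose". Sections 8.1 and 10.1 also name creatinine separately from the liver profile.

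**4. Day counts for the 90 mg/d arm.** The inputs come from "Table 1: Baclofen Titration and Dosing Schedule": full dose on days 12 to 94 and last active dose (10 mg) on day 106. Week *n* is taken as day 7*n*, so weeks 4, 8, 10, 12 and 16 fall on days 28, 56, 70, 84 and 112.

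- Days at full dose: 94 − 12 + 1 = 83.
- Liver checks at full dose: visit text, days 28 and 70 = 2; other three places, days 28, 56 and 84 = 3.
- Creatinine draws at full dose: visit text read literally = 0; other three places = 3.
- Last on-treatment liver check to week 16: visit text, 112 − 70 = 42 days; other three places, 112 − 84 = 28 days.
- Week 16 relative to the last active dose: 112 − 106 = 6 days after it.

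**5. Sensitivity to the day convention.** Counting week *n* as day 7*n* + 1 moves every visit one day later. The draw counts and the 42- and 28-day gaps do not change, and the last figure becomes 113 − 106 = 7 days.

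**The case against.** The strongest reply is that the intended schedule is plain. Three places agree against one sentence. Section 8.1 puts the weeks and the stopping rule in a single sentence, and section 10.1 puts its schedule immediately before its rule, so anyone applying either rule has the right weeks in front of them. The schedule table, which staff would naturally work from, agrees. To arrive at no creatinine draws, staff would have to ignore the table and both safety sections while still applying a rule that appears only in those sections. In addition, the visit text does not exclude creatinine. It merely fails to mention it, so on the analyte there is a gap and not a contradiction.

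Much of this stands. The zero-draw case is a worst case, conditional on the visit text being followed alone. The firmer contrast is two liver checks against three, with a final gap of 42 days against 28. The creatinine point is properly called an omission. The reply does not remove the conflict between week 10 and weeks 8 and 12, which nothing in the protocol resolves.

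**Conclusion.** The inconsistency is real: the visit text is out of line with three concordant places on timing, and it is silent on creatinine. The cost of following it is one fewer liver check during the 83 full-dose days of the 90 mg/d arm and a final interval 14 days longer (42 − 28). On a literal reading, there would also be no scheduled creatinine at full dose where three are intended. The first scheduled value after screening would then come about 6 days after the last active dose, unless the patient terminated early, and so too late to prompt stopping.

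These figures assume visits on their nominal days and the 90 mg/d titration table followed as written. The practical risk depends on which text a site uses, and the table makes the benign outcome more likely. The sentence should still be corrected, because it is an operative visit instruction that feeds the stopping rules for a renally cleared drug at high dose.

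**What to change.** Replace the sentence in section 6, Subsequent Treatment Visits, with: *Blood will be taken at weeks 4, 8 and 12 to measure AST, ALT, GGT, bilirubin, glucose and creatinine.* The weeks then match the table and sections 8.1 and 10.1. The analyte list is that of the table footnote, and it includes the creatinine that both safety sections require.

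The same amendment could settle a smaller mismatch at week 16. The table's asterisk limits that draw to the reduced panel, whereas the visit text asks for CBC and chemistries. This is a separate point, and the replacement sentence is right whichever way it is resolved.

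The cost is a one-sentence protocol correction, with no procedure added beyond those already in the schedule table.
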